### 9.5.1 Monitoring of COVID-19-Related Outcomes

**The incidence of COVID-19 diagnoses and hospitalizations (pooled over treatment groups) will be described as part of the routine (monthly) REPRIEVE adverse event monitoring reports and as targeted events at each DSMB review.**

## 9.6 Analyses

### 9.6.1 General Analysis Considerations

The following sections provide a brief overview of the analysis considerations for REPRIEVE (A5332). Prior to the start of enrollment, a detailed Statistical Analysis Plan fully delineates all planned statistical analyses. **In the event of a DSMB recommendation to stop the trial for efficacy at interim review, full analysis and publication of the primary trial results will be prepared based on the frozen data for the DSMB meeting. Subsequent analyses (including a database prepared for future data-sharing requests) will be performed based on the final trial database including all final study termination visits. In the event of a DSMB recommendation to stop for futility, full analysis and publication of the primary trial results will be performed based on the final trial database including all final study termination visits.**

All major treatment comparisons between the randomized groups will be performed according to the principle of "intention-to-treat;" that is, participants will be analyzed (and endpoints attributed) according to the randomized treatment assigned regardless of subsequent changes to that treatment; as-treated analyses will also be performed. Descriptive summaries of the distribution of continuous baseline variables will be presented in terms of percentiles (eg, median, 25th and 75th percentiles), while discrete variables will be summarized in terms of frequencies and percentages. Statistical comparisons will be performed using two-sided significance tests with a 5% Type I error.

Unless otherwise noted, comparison of time to event outcomes will use methods for competing risks, notably Cox proportional hazards models for estimation of cause-specific hazard ratios and Gray's test for comparison of cumulative incidence curves.

Treatment group comparisons of continuous outcomes will use t-tests with transformation as needed. In the event of non-Normal distributions even after transformation, Wilcoxon rank sum tests will be preferred. With respect to discrete outcomes, Wilcoxon rank sum tests will be used for ordinal outcomes; Chi-squared test will be used otherwise; Fisher's exact test will be preferred in the event of small cell numbers. All testing will be stratified by sex and CD4 cell count per randomization: while the primary analyses will not be further stratified by enrollment in the Mechanistic Substudy of REPRIEVE (A5333s), sensitivity analyses will be performed including this stratification. Additional perspective regarding the interpretation of the data will be provided through extensive use of confidence intervals and graphical displays.

Given the strong plans for participant follow-up as part of the study, it is anticipated that missing data will be minimized. Unless examination of the data suggest otherwise, missing data will be assumed to be ignorable; participants

lost to follow-up before experiencing a prior endpoint will be considered non-informatively censored. For all participants lost to follow-up, cardiovascular risk factors at the time of their final study visit will be described. In addition, a supportive analysis of time to death from any cause or MACE ([outcome measure 9.2.2.3](#)), including data from vital status and endpoint follow-up following premature study discontinuation will be conducted.

With the primary clinical and mechanistic hypotheses and the various secondary endpoints that have been outlined, it is recognized that there is a multiplicity of analyses to be performed, which leads to an increased probability that at least one of the comparisons could be "significant" by chance. Although the overall level of significance for all treatment comparisons will be 0.05, we will be conservative in the interpretation of our supporting analyses, taking into account the degree of significance, and looking for consistency across endpoints. Assessment will be made for any differences in major disease indices between participants in the Mechanistic Substudy of REPRIEVE (A5333s) and REPRIEVE (A5332). Such differences are unlikely, given that all participants in the Mechanistic Substudy will be eligible for REPRIEVE (A5332) and vice versa. Moreover, a subset of sites will be performing both and there will be overlap in the capacity to do both studies at selected sites. Nonetheless, we will analyze for any differences in the main and Mechanistic Substudy populations and account for any such differences in our interpretation of the Mechanistic Substudy and main study results.

#### 9.6.2 Primary **MACE** and Supportive Analyses

The primary comparison of study arms for the primary composite endpoint will be time to event analyses and therefore based on the time from randomization to the first of any of the components of the primary composite endpoint. Deaths from non-CVD causes will be treated as competing risk events and participants completing follow-up without experiencing the event will be considered censored at the time of their last contact at which an assessment for primary endpoints was made.

A Stratified **cause-specific** Cox proportional hazards model will be the primary analytic methods used for assessing outcome differences between the two treatment groups with stratification by sex and CD4 cell count at screening as previously noted. The relative cause specific hazard of pitavastatin versus placebo for MACE will be estimated with a **repeated** 95% confidence interval and compared via a Wald test; modification of the statin effect over time (non-proportional hazards) will be evaluated with treatment by time interaction. In supportive analyses, the cumulative incidence of MACE will be estimated **using the Breslow estimators of the cause-specific hazard from the Cox model and plotted** over time by treatment group and compared via a stratified Gray test.

To complement the primary analyses, the same analytic approach will be used for evaluation of individual components of the primary MACE endpoint. In the absence of a competing risk event, treatment comparisons of all-cause mortality and a composite of MACE and all-cause mortality will use a stratified log-rank test.

Poisson regression with robust variance estimates will also be used to incorporate multiple and repeated events in evaluation of event incidence rates by treatment group and rate ratios. Sensitivity analyses will be performed that censor individuals for whom critically significant CAD was identified as a result of the Mechanistic Substudy of REPRIEVE (A5333s) CCTA evaluation; censoring will occur at the date of the apparent CCTA study findings.

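### The supportive MACE cumulative-incidence curves come from the proportional-hazards Cox fit, so on the plain reading they cannot show a delayed or fading statin effect

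*Protocol*

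**What the plan says.** Protocol section 9.6.2 sets out the MACE analysis in one paragraph.

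- **Primary model.** The treatment comparison rests on a stratified, cause-specific fit: "Cox proportional hazards model will be the primary analytic methods used for assessing outcome differences between the two treatment groups". The strata are sex and screening CD4; treatment is not listed as one.
- **Treatment effect.** Pitavastatin is set against placebo as a relative cause-specific hazard, reported with a repeated 95% interval and tested by Wald.
- **Non-proportionality.** "modification of the statin effect over time (non-proportional hazards) will be evaluated with treatment by time interaction". The text does not carry the result of that evaluation into the figure.
- **Curves.** In supportive analyses the cumulative incidence is estimated "using the Breslow estimators of the cause-specific hazard from the Cox model and plotted". One curve is drawn for each arm, and a stratified Gray test compares them.
- **Competing event.** "Deaths from non-CVD causes will be treated as competing risk events". Section 9.2.1 narrows this to deaths from known non-CVD causes, because deaths of undetermined cause count as MACE.

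Section 9.6.1 gives the two tools separate jobs: "Cox proportional hazards models for estimation of cause-specific hazard ratios and Gray's test for comparison of cumulative incidence curves". Neither section names a by-arm non-parametric estimate of the MACE curves.

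**The concern.** If treatment is a covariate in the Cox fit, the model has one baseline hazard per sex-by-CD4 stratum and one multiplier for pitavastatin. Curves built from it have a fixed ratio of cause-specific cumulative hazards between arms at every time within a stratum, whatever the data show. The two arms separate from the first day in the proportion set by the average hazard ratio. Gray's test compares cumulative incidence without that restriction, so the figure and its companion test rest on different assumptions.

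The question is not idle in this trial. Section 9.4.1 models cross-over that dilutes an underlying efficacy of 0.66 to an average effectiveness of 0.70 over six years, and an effect that dilutes as cross-over builds up is not constant. The rationale in section 2.2 includes plaque stabilization, for which some delay is plausible. Follow-up may now run to 120 months.

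At stake is the picture of when benefit begins and how large it is in absolute terms in the early years. Section 9.6.2 uses the same approach for the individual MACE components, and section 9.6.3 uses it for the targeted serious clinical diagnoses. Under section 9.6.1, a stop for efficacy at an interim look would put the frozen interim data into the primary publication. The early part of the curve would then carry more weight.

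**Working it through.** **Inputs from the Protocol:** control rate 15/1000 PY and target hazard ratio 0.70 (section 9.4.1); 1:1 allocation (section 9.3); original total follow-up of 6 years (section 9.4.1).

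**Inputs assumed:** no statin effect in year 1, then a hazard ratio of 0.64. The 6-year average is (1 + 5 × 0.64)/6 = 4.2/6 = 0.70. Competing deaths, losses and staggered entry are left out of this first calculation.

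**The plan's own figures.** With a constant hazard ratio of 0.70, 5-year incidence is 1 − exp(−0.075) = 7.23% and 1 − exp(−0.0525) = 5.11%. The difference is 2.11 points and 1/0.0211 = 47, which is the 5-year NNT in section 9.4.1. Table 9.4.1-1 prints 7.3% and 5.1%. The 288-event target in section 9.4.2 also reproduces: (1.7/0.3)² × (1.960 + 1.036)² = 288.3.

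**Formulas.** Write Λ0 and Λ1 for the true cumulative hazards in the placebo and statin arms.

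- True incidence: 1 − exp(−Λ0) and 1 − exp(−Λ1).
- Breslow baseline from a fit with hazard ratio 0.70 and roughly equal numbers at risk: B = (Λ0 + Λ1)/(1 + 0.70).
- Drawn incidence: 1 − exp(−B) for placebo and 1 − exp(−0.70 × B) for statin.

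**Numbers put in.**

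- Year 1: Λ0 = Λ1 = 0.015, so B = 0.030/1.7 = 0.01765.
- Year 2: Λ0 = 0.030 and Λ1 = 0.015 + 0.0096 = 0.0246, so B = 0.0546/1.7 = 0.03212.
- Year 5: Λ0 = 0.075 and Λ1 = 0.015 + 4 × 0.0096 = 0.0534, so B = 0.1284/1.7 = 0.07553.

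| Year | True, placebo / statin | True difference | Drawn, placebo / statin | Drawn difference |
|---|---|---|---|---|
| 1 | 1.49% / 1.49% | 0 | 1.75% / 1.23% | 0.52 |
| 2 | 2.96% / 2.43% | 0.53 | 3.16% / 2.22% | 0.94 |
| 5 | 7.23% / 5.20% | 2.03 | 7.27% / 5.15% | 2.13 |

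Differences are in percentage points and were taken before rounding.

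**The other direction.** Assume a hazard ratio of 0.60 for three years and 0.80 for the next three, again averaging 0.70. At year 3, Λ0 = 0.045 and Λ1 = 0.027, so B = 0.072/1.7 = 0.04235. The true difference is 4.40% − 2.66% = 1.74 points and the drawn one is 4.15% − 2.92% = 1.23. A fading effect is understated early.

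**Check by simulation.** This used 300 trials of 7500 participants per scenario, with an assumed non-CVD death rate of 8/1000 PY and the sex and CD4 strata omitted.

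- Control 10/1000 PY (the lowest rate in Table 9.5-3), no effect for 2 years, then 0.5: about 311 events per trial. The by-arm Aalen-Johansen differences are 0.01, 0.01 and 1.38 points at years 1, 2 and 5. The Cox/Breslow curves from the same data give 0.36, 0.70 and 1.44.
- Control 10/1000 PY, constant hazard ratio 0.70: Aalen-Johansen gives 0.29, 0.56 and 1.35 points; Cox/Breslow gives 0.28, 0.56 and 1.35.
- In the 2-year-delay scenario the mean z-values were −3.15 (Cox) and −3.18 (Gray), with correlation about 1.0.

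In the matching large-sample calculation, varying the assumed non-CVD death rate over 3, 8 and 15/1000 PY moved the ratio of the drawn incidences by less than 0.01.

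Strictly, it is the cause-specific cumulative hazards that are exactly proportional. The drawn incidences are only nearly so: in the scenarios run, their ratio drifted by about 0.01 over seven years.

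**The case against.** The strongest reply is that section 9.6 is an overview. It defers to a main-trial SAP that is not among the documents supplied; the SAP here covers only substudy A5333s. If the curves come from a Cox fit stratified by treatment, the Breslow estimator becomes the Nelson-Aalen estimator by arm and the problem disappears. The same paragraph also plans a model with a treatment-by-time term and does not say outright which fit feeds the plot. This stands as a limit on certainty. The plain reading is still the primary model, because it is the one the paragraph has just described and nothing states a treatment-stratified fit.

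Several stronger inferences are tempting, and the documents do not support them.

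- *That the protocol itself doubts proportionality.* It says only that non-proportionality will be evaluated, which is a routine check.
- *That the Gray p-value is wrong.* Gray's test remains a valid comparison of the arms however the figure is drawn, and it nearly coincided with the Cox test in simulation. The mismatch lies between the test and the drawn curves.
- *That a planned NNT or yearly risk difference would be biased.* Section 9.6.2 plans neither from these curves. The design NNT is at 5 years, where the example gives 1/0.0203 ≈ 49 in truth and 1/0.0213 ≈ 47 as drawn.

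It is also fair that the distortion is modest against sampling error. With about 3750 per arm and complete follow-up, the standard error of the risk difference is about 0.28 points at year 1 and 0.37 at year 2. The shifts of 0.52 and 0.94 − 0.53 = 0.41 points are thus about 1.9 and 1.1 standard errors. They are, however, a systematic error that the reader of the figure cannot see.

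Finally, model-based curves agree with the reported hazard ratio and carry the stratification, which simple curves by arm do not. That is a reason to show them as an addition, clearly labelled.

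**Conclusion.** The point holds as a minor, cheap improvement. On the plain reading of section 9.6.2, the MACE figure imposes proportional cause-specific hazards and so cannot display the change over time that the same paragraph sets out to examine. With a one-year delay the drawn curves would show a year-1 gap of about 0.52 points where none exists and would overstate the year-2 difference (0.94 against 0.53). By year 5 the discrepancy is about 0.1 point.

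These sizes rest on the assumed delay and late hazard ratio, which the documents do not predict; with a constant hazard ratio there is no discrepancy. The analysis is supportive. The primary hazard ratio, its interval, the Wald test and the Gray p-value are untouched, and the treatment-by-time interaction is a partial check on a changing effect. The conclusion would fall away if the main-trial SAP specifies a fit stratified by treatment.

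**What to change.** Change the phrase in section 9.6.2 so that cumulative incidence is estimated and plotted by arm with the Aalen-Johansen estimator, with death from known non-CVD causes as the competing event. Breslow estimators from a Cox fit stratified by treatment are equivalent. Either version can be combined over the sex and CD4 strata if that is wanted; if so, state how. Take any absolute risks or risk differences from these curves, keep the Cox model for the hazard ratio, and label any model-based curve as such. Apply the same wording to the MACE components and to the section 9.6.3 outcomes that borrow the method. If the main-trial SAP already specifies a treatment-stratified fit, saying so in section 9.6.2 is enough.

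The cost is one phrase and standard software. The curves will be slightly less smooth.

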#### 9.6.3 Secondary **MACE** and **Lipid** Analyses

Analyses of targeted serious clinical diagnoses (see [section 9.2.2.4](#)) will use the same methods as described for the primary MACE endpoint for the composite and individual outcomes. Analyses of a further composite outcome including the primary MACE outcomes (the START endpoint) will also be performed.

Summary statistics (means and quantile distributions) will be provided to describe the distributions of LDL and non-HDL cholesterol from study entry and 12 month intervals over time. At each annual post-entry time point, the mean difference in levels between treatment groups will be estimated with 95% confidence interval. **Mixed effects models adjusted** for sex and screening CD4 cell count will be used for **repeated measurements over time to estimate annual treatment group differences**; the same analyses will be applied for other lipid fractions.

**Prognostic Factors of MACE:** Important secondary aims of REPRIEVE (A5332) are to evaluate whether baseline traditional risk factors and time updated HIV-specific risk factors are predictive of MACE and pitavastatin effects on MACE in the HIV population.

Targeted risk factors of interest at (or prior to) study entry and time-updated (as indicated) are as follows:

At study entry/screening:

- Age, sex, race
- **ASCVD risk score**
- HIV-1 RNA level
- CD4 cells count
- Nadir CD4 cell count
- Duration of ART exposure and any exposure to thymidine analogs, protease inhibitors, or abacavir

- Weight, BMI, waist circumference
- Fasting lipid (TC, HDL-C and LDL-C, HDL:LDL ratio, TG) and glucose
- Smoking status
- Systolic and diastolic BP and use of antihypertensive agents
- Presence of metabolic syndrome defined according to current guidelines at the time of the analysis.
- Self-reported level of physical activity
- Family history of heart disease

Time-updated (annually unless otherwise noted):

- HIV-1 RNA level
- CD4 cells count
- Fasting lipid (TC, HDL-C and LDL-C, HDL:LDL ratio, TG) and glucose and their changes expressed as absolute change and as percent of baseline

Analyses will use stratified Cox proportional hazards models to estimate the cause-specific hazard of MACE with respect to the risk factors of interest, including the selected biomarkers representing surrogates from plaque progression as described above. In the full cohort we will include the baseline risk factors and evaluate modification of the statin effect by key subgroups (ie, race/ethnicity sex, and CD4 cell count at screening as well as HIV-related and CV risk factors including age, hypertension, LDL and non-HDL cholesterol at entry, BMI, metabolic syndrome (as defined by current NCEP guidelines at the time of the analysis) and smoking) by interaction terms in these models.

This approach will investigate associations with LDL and non-HDL levels and changes from baseline as a time-updated covariate. The same approach to analysis will be used to assess the effects of other longitudinal outcomes. With respect to HIV-1 RNA levels over time, it is of particular interest to examine whether there is evidence of the modification of the effect of statins according to whether participants maintain full suppression of HIV-1 RNA levels. This will be examined in a 12-month landmarked Cox proportional hazards models assessing an interaction between continued HIV-1 RNA suppression (<400 copies/mL) over the first 12 months of the study as well as time-updated analysis. The analysis approach for assessment of effect of selected biomarkers for MACE will be determined based on the sampling approach to biomarker testing. Depending on power consideration, sampling may involve testing of the entire REPRIEVE (A5332) study population or a restricted sampling approach such as a case-cohort sampling. In this case, the same analytic approach as described above would be utilized with appropriate weighting for the sampling fractions; an alternative would be case-control sampling with analyses performed using logistic regression.

The frequency with which serious adverse events (excluding study defined clinical endpoints) occur will be tabulated and descriptively summarized.

Additional targeted and pre-specified adverse events that will be summarized will include incident diabetes, elevated liver function tests, and myositis. Statistical comparisons of the randomized arms with respect to adverse events will use chi-square or other appropriate two-sample methods depending on the nature of the event, interpreting such comparisons in the context of differences between the two randomized arms in the primary and major secondary clinical endpoints.

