- 5 At the screening visit, CD4+/CD8+ from clinical care within 180 days prior to entry will be used; if not available, this will be drawn as part of the study. For post-entry CD4+/CD8+, the most recent values obtained since the last annual visit will be used. At discontinuation visits, CD4+/CD8+ from clinical care within 180 days of that visit will be used.
- 6 For the entry visit, an HIV-1 RNA from clinical care from the prior 180 days will be used; if not available, do not collect. For post-entry evaluations, the most recent viral load obtained from clinical care since the last annual visit will be used. At discontinuation visits, plasma HIV-1 RNA from clinical care within 180 days of that visit will be used.
- 7 At the screening visit, results of CBC, creatinine, lipid panel, and ALT (and when needed per footnote #10, AST) will be obtained from clinical care if available within 90 days prior to entry; if not available, draw as part of the study. At discontinuation visits, CBC and creatinine from clinical care within 180 days of that visit will be used.
- 8 At the screening visit, direct LDL must be determined if triglyceride 400-500 mg/dL.
- 9 Fasting lipid panels, glucose, and plasma/serum for biomarkers from entry visit forward will be performed centrally. Participants may choose to opt out of these entry and post-entry labs.
- 10 AST is only required for persons with known chronic active HCV and/or HBV in order to calculate FIB-4 at screening. Use results from clinical care if available within 90 days prior to entry; if not available, draw as part of the study.
- 11 The urine for creatinine/albumin is required of all participants at entry. At months 12, 24, and 48, collect only for participants at ACTG sites who enrolled in REPRIEVE (A5332) prior to 01/01/2018.
- 12 Whole blood for genetic testing will be drawn at ACTG sites only.
- 13 Additional safety labs will be checked at the discretion of site investigator based on participant symptoms (see [section 7.1](#)).
- 14 Please refer to [section 6.3.10](#) for details.
- 15 Please refer to [section 6.4](#) for details.
- 16 **Hormonal/reproductive health assessments relevant to CVD risk will be determined at study termination/discontinuation visits.**

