### 9.2.2.5 Calculated fasting LDL and non-HDL cholesterol level at study entry and annually thereafter as well as change from baseline expressed as absolute change and as a percentage of baseline. For participants with triglycerides >400 mg/dL and <500 mg/dL, direct LDL will be determined and use in the statistical analysis.

9.2.2.6 Time to any of the following adverse events (including recurrent events as appropriate)

- Serious adverse event as defined by ICH criteria
- Incident Diabetes mellitus (DM)
- Grade 3 or 4 ALT
- Grade 3 or 4 myopathy
- **COVID-19 diagnosis**
- **Serious COVID-19 diagnosis (ie, a COVID-19 diagnosis that is Grade 4 or results in hospitalization or death)**

All events will be included regardless of relationship to treatment as determined by sites.

Grading will be defined per the DAIDS Table for Grading the Severity of Adult and Pediatric Adverse Events, corrected Version 2.1, July 2017.

See [section 11.4](#) for link to the document.

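### The protocol's lipid models adjust for sex and CD4 but do not name the entry lipid value, a modest and avoidable loss of precision

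*Protocol*

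**What the plan says.** Protocol section 9.6.3 sets out two treatment comparisons for LDL and non-HDL cholesterol. At each annual post-entry visit, "the mean difference in levels between treatment groups will be estimated with 95% confidence interval". In addition, mixed effects models adjusted "for sex and screening CD4 cell count will be used for" the lipid values collected across visits, to give a treatment difference for each year. Other lipid fractions are handled in the same way. The entry lipid value is named in neither comparison.

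The general rules in Protocol section 9.6.1 do not supply it. They state that "Treatment group comparisons of continuous outcomes will use t-tests with transformation as needed" and stratify testing by sex and CD4 count.

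The entry value is available. Protocol Table 6.1a, footnote 9, states that "Fasting lipid panels, glucose, and plasma/serum for biomarkers from entry visit forward will be performed centrally", and adds that "Participants may choose to opt out of these entry and post-entry labs". Protocol section 9.2.2.5 defines the outcome as "Calculated fasting LDL and non-HDL cholesterol level at study entry and annually thereafter as well as change from baseline expressed as absolute change"; percentage change is included too.

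The supplied SAP covers the mechanistic substudy (A5333s) only. Its section 7.1 bases inference on continuous outcomes on baseline-adjusted mean differences. Its section 3.6 makes lipids descriptive and leaves the statin effect on them to the full cohort.

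**The concern.** A participant's entry lipid value can be expected to predict the later values of the same lipid. A model that leaves it out keeps between-person variation in the error term that could be removed at almost no cost. Formal lipid inference rests on the main-trial models, because the substudy makes no formal lipid comparison. What is at stake is the width of the confidence intervals around the annual lipid differences, and power where those differences are small. The validity of the comparison is not in question.

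**Working it through.** **No figure to reproduce.** The documents give no sample size, standard deviation, correlation or precision target for any lipid comparison. The check is therefore of relative precision over an assumed range.

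**Inputs from the documents**
- 1:1 allocation (Protocol section 9.3) and about 7500 participants (section 9.4), so 3750 per arm before losses and opt-outs.
- Two-sided 5% tests (section 9.6.1).
- A within-person correlation of 0.65 from baseline to 1 year, given for sCD14 in Protocol Appendix IV (Objective 1, Hypothesis C). It is used here only as one point in a range.

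**Assumptions**
- Correlation ρ between entry and follow-up lipid values from 0.3 to 0.8.
- Equal variances at entry and follow-up, and complete data.
- Lipid standard deviation of 25 to 40 mg/dL.

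**Variance of the treatment difference at one annual visit, relative to levels**
- Levels: 1
- Absolute change from entry: 2(1 − ρ)
- Entry value as covariate: 1 − ρ²
- Covariate against change: (1 − ρ²) / [2(1 − ρ)] = (1 + ρ)/2

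| ρ | Change | Covariate | CI narrower vs levels, 1 − √(1 − ρ²) | CI narrower vs change, 1 − √((1 + ρ)/2) |
|---|---|---|---|---|
| 0.5 | 1.00 | 0.75 | 13% | 13% |
| 0.65 | 0.70 | 0.58 | 24% | 9% |
| 0.7 | 0.60 | 0.51 | 29% | 8% |

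At the ends of the range, the covariate form multiplies the interval width for levels by 0.95 (ρ = 0.3) and 0.60 (ρ = 0.8).

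**If entry is one of the repeated responses.** A generalized least squares calculation with six annual visits and compound symmetry gives a relative variance at ρ = 0.65 of:
- 1.00 when the arms may differ at entry, which is no gain over levels;
- 0.58 when both arms share one entry mean, the same as the covariate form.

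**In mg/dL.** With SD 30 and 3750 per arm, the 95% half-width for levels is 1.96 × 30 × √(2/3750) = 1.36. At ρ = 0.65 it is 1.36 × √0.70 = 1.14 for change and 1.36 × √0.58 = 1.03 with the entry value.

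**Power, levels against entry-adjusted at ρ = 0.65**
- N = 7500, difference 5 mg/dL: above 99.9% without adjustment for SD 25 to 40.
- N = 7500, difference 3 mg/dL: 99.9%, 99.1% and 90.1% without adjustment at SD 25, 30 and 40. At SD 40, adjustment raises 90.1% to 99.0%.
- If only 3000 participants had lipid data (an assumption), difference 3 mg/dL and SD 30: 78% rises to 95%.

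**The case against.** **Section 9.6 is an overview.** Section 9.6.1 says so and defers to a detailed SAP. The main-trial SAP was not available, so it may already specify the entry value. That limits the point to the protocol text, but nothing in the supplied documents describes a baseline-adjusted lipid model.

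**The mixed model may already use entry as a response.** Section 9.6.3 describes lipids from study entry onward before it introduces the repeated-measures model. This would recover the full gain only with a common entry mean across arms, and no such constraint is described. With arms free to differ at entry there is no gain. The ambiguity is itself a reason to state the model.

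**Change from baseline is part of the outcome.** This stands, and it reduces the size of the point. At ρ = 0.65 the intervals narrow by 9% against absolute change, not 24%. Change scores also remove most of the worry about chance imbalance at entry when ρ is high.

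**The practical effect is small at full size.** This also stands. LDL power is near 1, and HDL, total cholesterol and the LDL-to-HDL ratio are exploratory (Protocol section 9.2.3.1).

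**An entry covariate has a cost.** Participants who opted out of the entry sample would drop out of the model unless their missing values were handled.

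A reader might also infer that the precision of the LDL comparison carries into the objective linking LDL to MACE. It does not. Section 9.6.3 enters each participant's own LDL level and change as a time-updated covariate in Cox models, and the between-arm estimate is not an input. Nor does the substudy SAP show lipids being compared with baseline adjustment, since it makes no formal lipid comparison.

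**Conclusion.** The point holds as a low-severity matter of efficiency. The protocol names sex and screening CD4 as the only adjustments in the lipid mixed models and leaves out an entry value that the trial collects. For assumed correlations of 0.5 to 0.7, intervals would be about 13% to 29% narrower than with levels and about 13% to 8% narrower than with absolute change. These sizes rest on assumed correlations, equal variances and complete data. The only correlation used that comes from the documents, 0.65, is for sCD14.

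Two stronger conclusions are not supported. The lipid estimates are not biased, because randomization protects the unadjusted comparison. The LDL result is not at risk at about 7500 participants. The gain is of practical use for small differences in other fractions, or if opt-out leaves far fewer participants with lipid data. The documents do not give the extent of opt-out.

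**What to change.** In Protocol section 9.6.3, specify one of two forms for every lipid mixed model:

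1. the entry value of that lipid and its interaction with visit as covariates, in addition to sex and screening CD4; or
2. entry as one of the responses, with a common entry mean across arms and treatment effects at post-entry visits only.

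Report the resulting annual differences as the main lipid comparison, with the raw differences in levels as description.

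The cost is a model term and a sentence of text, with no new data. The second form keeps participants who have no entry sample but have follow-up samples. The first needs a stated rule for missing entry values. If the main-trial SAP already specifies either form, the only action is to align the protocol with it.
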